5.1 Inclusion Criteria

A subject is eligible for the study if all the following apply:

1. Institutional Review Board (IRB)/Independent Ethics Committee (IEC) approved written Informed Consent and privacy language as per national regulation (e.g., Health Insurance Portability and Accountability Authorization for US sites) must be obtained from the subject or legally authorized representative prior to any study-related procedures (including withdrawal of prohibited medication, if applicable).
2. Subject must be 18 to 75 years of age at the time of informed consent.
3. Subject has chronic tympanic membrane perforation (CTMP) documented as persisting longer than 3 months.
4. A female subject is eligible to participate if she is not pregnant see Appendix [12.3: Contraception Requirements](#) and at least one of the following conditions applies:
 - a. Not a woman of childbearing potential (WOCBP) as defined in Appendix [12.3: Contraception Requirements](#) OR
 - b. WOCBP who agrees to follow the contraceptive guidance as defined in Appendix [12.3: Contraception Requirements](#) starting at screening and for at least 28 days after investigational product (IP) application.
5. Female subject must agree not to breastfeed starting at drug application on Day 1 and for at least 28 days after IP application.
6. Female subject must not donate ova starting on Day 1 and for at least 28 days after IP application.
7. A male subject with female partner(s) of child-bearing potential must agree to use contraception starting on Day 1 and for at least 28 days after IP application as detailed in Appendix [12.3](#).
8. A male subject must not donate sperm starting on Day 1 and for at least 28 days after IP application.
9. Male subject with a pregnant or breastfeeding partner(s) must agree to remain abstinent or use a condom from Day 1 and for at least 28 days after IP application.
10. Subject must be willing and able to comply with the study requirements including refraining from using prohibited concomitant medications.
11. Subject agrees not to participate in another interventional study during the study period.

12. Subject has the ability to understand and the willingness to sign a written informed consent document.

Waivers to the inclusion criteria will NOT be allowed.

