5.2 Exclusion Criteria

A subject will be excluded from participation if any of the following apply:

1. Subject has one of following conditions, that is confirmed by the investigator, that may affect the ipsilateral side of the ear with CTMP:
 - a. Perforation involving 3 or more quadrants.
 - b. Pin hole perforation (only for the expansion cohort).
 - c. Presence of tympanosclerosis adjacent to the perforation.
 - d. Perforation involves malleus erosion.
 - e. Absent malleus.
 - f. Marginal perforation (i.e., involving the annulus or exposing the handle of malleus).
 - g. TMP caused by electric/slag/blast/burn injury.
 - h. Post radiated TMP.
 - i. History of tympanic membrane repair by any type of live tissue.
 - j. Active otorrhea or active treatment for otorrhea within the last 3 months prior to Screening.
 - k. Bellucci otorrhea grade 3 or above.
 - l. Active external ear canal inflammation (otitis externa, dermatitis) or within the last 3 months prior to Screening.
 - m. Active diagnosis of Eustachian Tube dysfunction or diagnosis within 6 months prior to Screening.
 - n. Craniofacial abnormalities, history of head and neck surgery within the last 3 months prior to Screening, history of radiation to head and neck.
 - o. Recent (within 2 weeks) diagnosis of upper respiratory tract infection.
 - p. Presence or history of cholesteatoma.
 - q. Presence of pars-flaccida or pars tensa retraction or adhesion.
 - r. Presence or history of tumors of the middle or external ear.
 - s. Contraindications to tympanic membrane closure.
 - t. An audiometric finding indicates a characteristic of Carhart's notch which is an increase in bone conduction threshold with a peak at 2,000 Hz.
 - u. Only hearing ear or better hearing ear and the contralateral ear ≥ 40 dB by average four-frequency (500, 1000, 2000 and 4000 Hz).
 - v. Whole circumference of the tympanic membrane perforation is not visible by endoscope.
 - w. Presence/history of eosinophilic otitis media in either ear.
2. Subject has a presence of adhesive otitis media in the contralateral ear.
3. Subject has a presence of any wound healing systemic condition.

4. Subject has Obstructive Sleep Apnea where the subject is required to use Continuous Positive Airway Pressure (CPAP) during the study period.
5. Subject is exposed in their daily life to high volume of water into the ear canal (e.g., swimmer or surfer).

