9.4.3 Analysis of Exploratory Endpoints

SAD and single dose expansion

Categorical endpoints:

- Complete closure of TMP for post baseline visits at Day 2, Day 3 (evaluations at this visit will only be performed for cohorts 1, 2 and 3), Week 1, Week 2, and Week 4 for SAD and Week 2, Week 4, and Week 8, for dose expansion.
For observed response definition, refer to Section [9.4.2](#).
- Size of TMP $\leq 5\%$ of pars tensa surface area after treatment.
Observed response is defined as follows using the non-missing result:
Yes: if the post-baseline size of the TMP per pars tensa surface area $\leq 5\%$ and the size of the TMP per pars tensa surface area is smaller than baseline
No: if the above condition is false
- Size of TMP $\leq 1\%$ of pars tensa surface area (pin point perforation) after treatment.
Observed response is defined as follows using the non-missing result:
Yes: if the post-baseline size of the TMP per pars tensa surface area $\leq 1\%$ and the size of the TMP per pars tensa surface area is smaller than baseline
No: if the above condition is false
- Percentage improvement from baseline in A-B gap by PTA $\geq 50\%$ (improvement of conductive hearing).
For A-B gap, decrease (reduction) from baseline indicates an improvement.
Observed response is defined as follows using the non-missing result:
Yes: if the percentage change from baseline in mean A-B gap (derived using mean of the A-B gap results at 500 Hz, 1, 2 and 4 kHz) $\leq -50\%$
No: if the above condition is false
- Improvement from baseline in air conduction hearing by PTA ≥ 15 dB.
For air conduction hearing, decrease (reduction) from baseline indicates an improvement.
Observed response is defined as follows using the non-missing result:
Yes: if the change from baseline in mean air conduction hearing by PTA (derived using mean of the results at 500 Hz, 1, 2 and 4 kHz) ≤ -15 dB
No: if the above condition is false
- A-B gap after treatment was 15 dB or less.
Observed response is defined as follows using the non-missing result:
Yes: if the post baseline result in the mean A-B gap (derived using mean of A-B gap results at 500 Hz, 1, 2 and 4 kHz) ≤ 15 dB
No: if the above condition is false
- Air conduction hearing threshold after treatment was 30 dB or less.
Observed response is defined as follows using the non-missing result:
Yes: if the post baseline result in mean air conduction hearing threshold by PTA (derived using mean of results at 500 Hz, 1, 2 and 4 kHz) ≤ 30 dB

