Air conduction hearing at the frequency level - bone conduction hearing at the frequency level. If either one is missing or both are missing then the A-B gap is set to missing. This will be derived for frequencies 500 Hz, 1 kHz, 2 kHz, and 4 kHz.

- Change from baseline in air conduction hearing by PTA

Mean air conduction hearing will be derived as explained in the endpoint Percentage improvement from baseline in A-B gap by PTA $\geq 50\%$ (improvement of conductive hearing)

- Percentage improvement from baseline in A-B gap by PTA $\geq 50\%$ (improvement of conductive hearing)

Observed response:

Using the non-missing percentage change from baseline in mean A-B gap, an observed response is

Yes: if the percentage change from baseline in mean A-B gap (derived using mean of the A-B gap results at 500 Hz, 1, 2 and 4 kHz) $\leq -50\%$,

No: if the above condition is false.

- Improvement from baseline in air conduction hearing by PTA ≥ 15 dB
For the change from baseline in air conduction hearing, a negative value (decrease from baseline) indicates an improvement.

Observed response:

Using the non-missing change from baseline mean air conduction hearing, an observed response is

Yes: if the change from baseline in mean air conduction hearing by PTA ≤ -15 dB,
No: if the above condition is false.

- A-B gap after treatment was 15 dB or less

Observed response:

Using the non-missing mean A-B gap, an observed response is

Yes: if the post baseline mean A-B gap ≤ 15 dB,
No: if the above condition is false.

- Air conduction hearing threshold after treatment was 30 dB or less

For the air conduction hearing, a lower value indicates better hearing threshold.

Observed response:

Using the non-missing mean air conduction hearing, an observed response is

Yes: if the post baseline mean air conduction hearing ≤ 30 dB,
No: if the above condition is false.

- Type of tympanogram (A, B or C)
For Type A, there are 2 additional subcategories: Ad and As.
- Equivalent ear canal volume (ECV) by tympanometry

Safety endpoint:

- Vital signs (body temperature, blood pressure and pulse rate)
- Microscopic ear examination

At screening, both ears will be examined microscopically to identify the TMP and evaluate the eligibility of the subject for the study. Only treated ear will be examined at Day 1 and the following visits.

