Paper patch to treat the treated ear	Categorical	
 • Yes • No
Stratification factor TMP size group (expansion only)	Categorical	
 • $\leq 15\%$ • $> 15\%$
Targeted Medical History		
Tobacco history	Categorical	
 • Yes (Current) • No (Former or Never) 
 ◦ Former ◦ Never
Diabetes history	Categorical	
 • Yes • No
Latex allergy history	Categorical	
 • Yes • No
Latex sensitivity history	Categorical	
 • Yes • No
Cannabis History		
History of Cannabis Use	Categorical	
 • Current • Former • Never

Baseline variables:

Variable	Variable Type	Categories
Secondary Variables:		
Baseline ratio of TMP size group per total area of tympanic membrane from central imaging	Categorical	
• $\leq 15\%$• $> 15\%$
Baseline TMP size from central imaging	Continuous	NA
Baseline ratio of TMP size per total area of tympanic membrane from central imaging	Continuous	NA
Other Efficacy Variables:		
Baseline mean air conduction hearing loss by PTA	Continuous	NA
Baseline mean air conduction hearing loss group by PTA	Categorical	
• Normal (≤ 25 dB)• Mild hearing loss (> 25 to ≤ 40 dB)• Moderate hearing loss (> 40 to ≤ 55 dB)• Moderately severe hearing loss (> 55 to ≤ 70 dB)• Severe hearing loss (> 70 to ≤ 90 dB)• Profound loss (> 90 dB)

Medical history is coded in Medical Dictionary for Regulatory Activities (MedDRA) and will be summarized by System Organ Class (SOC) and Preferred Term (PT) for the SAF by treatment group, ASP0598 total (if applicable) and 'Total' over all treatment groups.

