Imputed response for complete closure of TMP as assessed by site investigator	
SAD: Week 8
 
Single dose expansion: Week 12 primary analysis and Week 12 sensitivity analysis
 
MAD: Week 12
 
Multiple dose expansion: Week 12 and Week 16 primary analysis and Week 16 sensitivity analysis

Imputed response for complete closure of TMP as assessed by central reader	
SAD: Week 8
 
Single dose expansion: Week 12 primary analysis and Week 12 sensitivity analysis
 
MAD: Week 12
 
Multiple dose expansion: Week 12 and Week 16 primary analysis and Week 16 sensitivity analysis

Reduction from baseline in size of TMP to less than or equal to 5% of pars tensa surface area 
 ● Observed response ● Observed response where subjects with $\leq 5\%$ at baseline are excluded 	
SAD: Week 8 and EOS
 
Single dose expansion: Week 8, Week 12 and EOS
 
MAD: Week 12 and EOS
 
Multiple dose expansion: Week 12, Week 16 and EOS

Reduction from baseline in size of TMP to less than or equal to 1% of pars tensa surface area 
 ● Observed response ● Observed response where subjects with $\leq 1\%$ at baseline are excluded 	
Observed response for percentage improvement from baseline in A-B gap by PTA $\geq 50\%$ (improvement of conductive hearing)	
Observed response for improvement from baseline in air conduction hearing by PTA $\geq 15\text{ dB}$	
SAD: Week 8 and EOS
 
Single dose expansion and MAD: Week 12 and EOS

Observed response for A-B gap after treatment was 15 dB or less	
Multiple dose expansion: Week 16 and EOS

Observed response for air conduction hearing threshold after treatment was 30 dB or less	
Type of tympanogram	
SAD: Baseline, Week 8 and EOS
 
Single dose expansion and MAD: Baseline, Week 12 and EOS
 
Multiple dose expansion: Baseline, Week 12, Week 16 and EOS

*Day 3 evaluations will only be performed for cohorts 1, 2 and 3

Table 2 Continuous Efficacy Variables for Descriptive Statistics

Variable	Plots	Analysis Visits
Ratio of TMP size per total area of tympanic membrane	SAD and MAD: Mean +/- SE for the change from baseline vs Analysis Visit by treatment group (overlay)	SAD: Baseline, Day 2, Day 3 ^b , Week 1, Week 2, Week 4, Week 8 and EOS

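### Two of the four exploratory hearing responders count ears already in target at baseline, and the 50% gap rule has no handling for a zero or negative baseline gap

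*SAP*

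**What the plan says.** **Entry.** The disease criterion in Protocol 5.1 is "Subject has chronic tympanic membrane perforation (CTMP) documented as persisting longer than 3 months". None of the inclusion criteria sets an air threshold or an air-bone (A-B) gap. The only exclusion with a decibel limit, 1.u in Protocol 5.2, begins "Only hearing ear or better hearing ear and the contralateral ear" and is triggered when that other ear is at 40 dB or more. It sets no minimum loss in the treated ear. Under Protocol 4.1, worse hearing serves only to choose between two eligible ears in bilateral disease.

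**Attained-level rules.** SAP 5.4 gives "Yes: if the post baseline mean A-B gap" at or below 15 dB, and "Yes: if the post baseline mean air conduction hearing" at or below 30 dB. Neither refers to baseline. Protocol 9.4.3 has the same rules, for example under "A-B gap after treatment was 15 dB or less".

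**Change rules.** The other two hearing responders are change-based: a fall of at least 15 dB in mean air conduction, and "Yes: if the percentage change from baseline in mean A-B gap" is −50% or lower. SAP 5.4 defines the mean gap as mean air minus mean bone conduction, with no floor at zero and no rule for a zero or negative baseline.

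**Size responders, for contrast.** In SAP 5.4 the 5% and 1% perforation-size responders also require a size below baseline. Table 1 in SAP 6.4 gives each a second version, "Observed response where subjects with" a baseline already at or under the cut-off left out. The hearing rows in Table 1 have the plain observed response only.

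**The concern.** A responder percentage reads as the share of ears that got better. If an ear can enter with its gap or air threshold already inside the target, the two attained-level endpoints record a response that treatment did not produce. Such ears raise the percentage in both arms, which shrinks any real difference. With small arms, chance imbalance in baseline hearing can also look like an effect. Randomization in the expansion is stratified on perforation size, so it does not balance hearing.

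The 50% rule has a different weakness. A percentage change behaves sensibly only when the baseline is positive. The gap here is a difference of two measured means, so zero and negative values are possible, and the SAP is silent on them.

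**Working it through.** **The plan's own figure.** The documents compute nothing for the hearing endpoints. The only computed design figure is for complete closure (Protocol 9.1, SAP 3): 10% vs 80%, two-sided 0.05, 11 per group, 13 after 10% drop-out. It reproduces: exact Fisher power at 11 per group is 90.5%, and 11/0.9 = 12.2, rounded up to 13. It is used below only as the source of 13 per arm and of illustrative rates.

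**1. Attained-level rules applied to single ears** (constructed values)

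| Air, dB | Bone, dB | Gap, dB | Gap ≤ 15 | Air ≤ 30 |
|---|---|---|---|---|
| 15 → 15 | 15 → 15 | 0 → 0 | Yes | Yes |
| 25 → 27.5 | 15 → 15 | 10 → 12.5 | Yes | Yes |

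The first ear did not change. In the second, air conduction worsened and the gap widened. Both are responders on both endpoints.

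**2. The 50% rule.** Percentage change = 100 × (post − baseline)/baseline. This is the standard formula, assumed because the SAP does not write it out.

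- Baseline −2.5, post 5: 100 × 7.5/(−2.5) = −300%, scored *Yes* although the gap widened.
- Air 15 → 20 with bone at 20: gap −5 → 0, 100 × 5/(−5) = −100%, scored *Yes* although air conduction worsened.
- Baseline 0: undefined. The rule uses non-missing percentage changes, so the subject silently leaves the denominator.

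**3. Size of one ear.** 1/13 = 7.7 points in an expansion arm. A 3 vs 1 split gives (3 − 1)/13 = 15.4 points with no treatment effect. In a SAD cohort with 4 active subjects, one ear is 1/4 = 25 points.

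**4. Chance imbalance.** Let f be the share of ears in target at baseline. The documents do not give f, so a range is assumed. With two independent arms of 13 and no treatment effect, the SD of the difference in in-target percentage is 100 × √(2f(1 − f)/13).

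| f (assumed) | Expected per arm, 13f | SD, points | Chance of arms differing by ≥ 2 ears (15.4 points) |
|---|---|---|---|
| 0.1 | 1.3 | 11.8 | 31% |
| 0.2 | 2.6 | 15.7 | 46% |
| 0.4 | 5.2 | 19.2 | 55% |

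**5. Dilution.** If in-target ears stay in target, the observed rate is f + (1 − f)p, where p is the response rate among the other ears. The difference between arms is therefore multiplied by (1 − f). With 10% vs 80%, borrowed from the closure assumption purely for illustration:

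- f = 0: 10% vs 80%, 70 points
- f = 0.2: 28% vs 84%, 56 points
- f = 0.5: 55% vs 90%, 35 points

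Excluding in-target ears restores 70 points at every f, with about 13 × (1 − f) ears per arm.

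**The case against.** The strongest reply is that nothing formal rests on these percentages. SAP 6.4.3 makes the categorical exploratory endpoints purely descriptive. The one planned analysis linking hearing to perforation is a regression of change in mean gap on change in the size ratio. It is continuous and baseline-referenced, so these rules do not touch it. A reader might infer that the planned link between hearing and perforation size is compromised; the documents do not support that.

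Baseline hearing will also be visible. SAP 6.2.3 tabulates "Baseline mean air conduction hearing loss group by PTA", Table 2 gives baseline, post-baseline and change for mean air conduction and mean gap plus individual plots, and SAP 6.4.3 adds a shift table. This stands as mitigation but is partial. The shift table's cut-offs are 25, 40, 55, 70 and 90 dB rather than 30, and the gap has no shift table. SAP 6.4 says in general that baseline values of categorical endpoints are summarized, yet Table 1 lists no Baseline visit for these rows.

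Three other stronger readings are tempting:

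- *All the hearing responders count in-target ears.* Only two of four do. The 15 dB improvement rule has the reverse limit: a near-normal ear has little room to gain 15 dB.
- *The Normal category (25 dB or less) shows that normal-hearing ears are expected.* The SAP 6.2.3 table also lists three or more involved areas and ages up to 84, which Protocol 5.2 and 5.1 exclude. A listed category shows only that such ears are not ruled out.
- *The 50% rule commonly scores worsening as improvement.* The route shown needs mean air conduction better than mean bone conduction at baseline. The documents give no frequency for that, and it may be rare.

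Attained level is also a legitimate measure in its own right, which is a reason to keep the existing rows.

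**Conclusion.** The point holds in limited form. The two attained-level hearing responders count ears that had nothing to correct, including ears that worsen within target, and the SAP's own safeguards for the size responders are missing here. The 50% rule has a real but probably uncommon gap at zero and negative baselines, given the standard percentage-change formula.

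The reach is descriptive exploratory output: 7.7 points per ear at 13 per arm, with a total effect that depends on an unknown share of in-target ears. The 25-point SAD figure carries little weight, since Protocol 9.1 says that part is not meant to show a difference. Nothing in the documents ties these percentages to a test, an error rate or a stated decision rule. The change is still worth making: at these arm sizes the placebo arm cannot correct a chance imbalance in baseline hearing.

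**What to change.** In SAP 5.4 and Table 1:

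1. Keep the existing 15 dB gap and 30 dB air-conduction rows.
2. Beside each, add the observed response with subjects excluded whose baseline mean A-B gap is 15 dB or less (or whose baseline mean air conduction is 30 dB or less). Show the number excluded per arm. No below-baseline condition is needed in these rows, because any value within target is then already lower than baseline.
3. For the 50% rule, write out the formula, limit the denominator to subjects with a baseline mean gap above zero, report how many are left out, and require the post-baseline gap to be below baseline. With a positive baseline that last condition follows from the arithmetic, so it serves as a programming check. Any higher minimum baseline belongs in a supplementary row only, since a 15 dB floor would discard genuine gains such as 12 to 4 dB.

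No entry criterion, visit or assessment changes, and the data are already collected. The cost is a smaller denominator in the added rows and in the 50% rule. At an assumed 40% in target, 13 × 0.6 = 7.8, so about 8 ears remain per arm and each moves the percentage by 1/8 = 12.5 points.

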6 STATISTICAL METHODOLOGY

6.1 General Considerations

Continuous data will be summarized descriptively including the number of subjects (n), mean, standard deviation (SD) and/or standard error, median, minimum and maximum.

Categorical data will be summarized by frequencies and percentages. Percentages by categories will be based on the number of subjects with no missing data, i.e. the percentages for the non-missing categories will add up to 100%.

For SAD and MAD, results will be presented by ASP0598 treatment group in each cohort and placebo group where placebo subjects will be pooled across cohorts.

For single dose expansion and multiple dose expansion, results will be presented by each ASP0598 treatment group and placebo group.

All statistical comparisons between ASP0598 and placebo will be conducted using 2-sided tests at $\alpha = 0.05$ significance level, unless stated otherwise. For dose expansion phase, a hierarchical testing method will be used to control familywise error rate where the highest dose group vs placebo will be tested first. Refer to Section [6.4.2](#) for details.

All data summarization and analyses will be performed using SAS® Version 9.4 or higher on Redhat Enterprise Linux. Specifications for tables, listings, and figures (TLF) formats can be found in the TLF specifications.

6.2 Study Population

6.2.1 Disposition of Subjects

The following subject data will be presented. Unique subjects are defined as rescreened subjects for whom the data from the last enrollment are used.

- Number of subjects with informed consent, unique subjects with informed consent, subjects with rescreening, subjects discontinued before randomization, unique subjects who discontinued before randomization and randomized for all subjects with informed consent (overall only),
- Screening disposition for all unique subjects with informed consent (overall only),
- Number and percentage of subjects who were randomized, were administered study drug, were not administered study drug, in the analysis sets by treatment group, ASP0598 total and ‘total’ over all treatment groups for all randomized subjects,
- Treatment disposition for all randomized subjects, SAF and FAS by each treatment group, ASP0598 total and ‘total’ over all treatment groups,
- Investigational period disposition for all randomized subjects, SAF and FAS by each treatment group, ASP0598 total and ‘total’ over all treatment groups, and
- Protocol version disposition for all unique subjects with informed consent by each treatment group and ‘total’ over all treatment groups for all randomized subjects, screen failures only and overall including screen failures,
- Number and percentage of subjects by site and country by treatment group and ‘total’ over all treatment groups for all randomized subjects.
- Number and percentage of subjects discontinued (cumulative by analysis visit) the study investigational period by analysis visit (Weeks 2, 4 and 8 for SAD, Weeks 2, 4, 8 and 12 for single dose expansion, Weeks 1, 2, 3, 4, 5, 8 and 12 for MAD, Weeks 2, 4, 6, 8, 12 and 16 for multiple dose expansion) and completed the study investigational period by

each treatment group for the FAS. For analysis visit windows, refer to [Table 6](#). For Week 2 SAD visit window will be same as Week 2 single dose expansion window.

